3.2.2.2 Derivations

Not applicable.

3.2.2.3 Handling of Dropouts and Missing Data

The analysis populations will only include participants who have completed three doses of study intervention and have baseline and post-benralizumab treatment study evaluation (PROs, CT scans, and spirometry tests). To that end, participants withdrawing before Week 13 and participants with one of the two FRI measurements missing will not be included in the analysis.

3.2.2.4 Primary Analysis of Secondary Endpoint 1

For each secondary FRI endpoint listed in Table 2, a paired t-test will be used to assess whether there is a statistically significant difference in the mean value at Week 0 versus Week 13, without adjustments for participant characteristics. Data will be log-transformed prior to analysis if there is evidence of skewness.

3.2.2.5 Secondary Analysis of Secondary Endpoint 1

For the secondary analysis of the secondary endpoint, a mixed-effects model will be employed to incorporate the repeated measurements (corresponding to the different lobes) for each subject. The fitted model will be provide estimates of the average percent change from baseline per lobe, with lobe as a fixed effect and a patient-level random effect to estimate the heterogeneity across lobes. The model will adjust for the baseline value of the secondary endpoint. The model will take the same form as described in Equation 1, but with "mucus volume" replaced by the secondary outcome of interest.

3.2.2.6 Sensitivity Analyses of the Secondary Endpoint

Not applicable.

3.2.2.7 Supplementary Analyses of the Secondary Endpoint

Not applicable.

3.2.2.8 Subgroup Analyses

Subgroup analyses will be carried out as described in Section 3.2.1.8.

3.2.3 Secondary Endpoint 2 – Correlation Between Airway Dynamics and Lung Functions Measurements at Week 0

3.2.3.1	Definition

Table 6Definition of Secondary Endpoint 2

Population:	Baseline endpoints analysis set	
Endpoint:	 Baseline (Week 0) relationship between: pre-BD FEV₁ and each FRI parameter (primary and secondary) 	
	• pre-BD FVC and each FRI parameter (primary and secondary)	
Treatment:	Benralizumab 30 mg, 3 doses, once every 4 weeks (at baseline [V1], Week 4 [V2] and Week 8 [V3])	
Intercurrent events:	Participant withdrawal, IPD, use of prohibited medicines/substances, asthma exacerbation	
Population-level	Spearman's rank correlation coefficients	
summary:	Pearson correlation	
	Graphical summary (scatterplots)	
	Regression coefficients with 95% CI	

3.2.3.2 Derivations

Not applicable.

3.2.3.3 Handling of Dropouts and Missing Data

Participants with missing baseline (Week 0) measurements do not form part of the analysis populations and so will not be included in the analysis.

3.2.3.4 Primary Analysis of Secondary Endpoint 2

Scatterplots will be used to display values of each imaging endpoint (including: all FRI endpoints in Table 2) against conventional lung function measures (including: pre-BD FEV₁ and pre-BD FVC response) at Week 0, to get a first indication of the relationship between endpoints at baseline.

Spearman's rank correlation coefficients will describe the strength of the association between each pair of FRI endpoints and conventional lung function measures. If the relationships appear linear, Pearson correlation will also be used. Correlation coefficients will be reported together with 95% CIs and p-values, testing the null hypothesis of no correlation. Standardized residuals will be used to check for linearity. If the linearity assumptions hold and if the two endpoints are correlated as per Pearson's p-value, a linear regression model will be used to estimate the average increase in each imaging endpoint per unit increase in conventional lung function measures, with 95% CIs. Two regression models per imaging parameter will be performed: one for the association with pre-BD FVC and one for the association with pre-BD FEV_1 at Week 0.

The linear regression model will be as follows:

$$y_i = \beta_0 + \beta_1 x_{1i}$$

where

- y_i is the value of the imaging endpoint at Week 0
- β₀ is the intercept
- x_{1i} is the value of the conventional lung function measure at Week 0
- β_1 quantifies the association as the average change in Y for every one unit increase in x_{1i}

Two models will be fitted for each imaging endpoint, Y, where model (i) takes x_1 to be pre-BD FEV₁ at Week 0 and model (ii) takes x_1 to the pre-BD FVC at Week 0.

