3 OBJECTIVES AND OUTCOME MEASURES

Table 2 Objectives and Outcome Measures

See footnote for abbreviations mentioned on the table below.

Obj	jectives	Outcome measures ^a							
Prir	nary								
dyn ben airv	describe the change from baseline in airway amics after 13 weeks following treatment with ralizumab, using total mucus volume (specific way volume) measurements from untrimmed ways.	Unadjusted mean within subject difference in total mucus volume measured at TLC, calculated as the mean change from baseline (week 0) at week 13 (\pm 5 days).							
Sec	ondary								
1.	To describe the change from baseline in airway dynamics at week 13 following treatment with benralizumab, as measured by secondary FRI endpoints ^b , irrespective of patient characteristics.	Unadjusted mean within subject difference in secondary FRI endpoints (total mucus plugs score at TLC; total air trapping at FRC; trimmed distal iVaww at TLC; trimmed distal siVaw at TLC and FRC; total iVlung at TLC and FRC), comparing baseline (week 0) to week 13 (± 5 days).							
2.	To describe the relationship between airway dynamics and conventional lung function measurements, cross-sectionally (at week 0) and irrespective of patient characteristics.	Correlation between imaging endpoints (primary and secondary FRI endpoints ^b) and pre-bronchodilator forced expiratory volume in 1 second (pre-BD FEV ₁) at week 0. Correlation between imaging endpoints (primary and secondary FRI endpoints ^b) and pre-bronchodilator forced vital capacity (pre-BD FVC) at week 0. Scatter plots of primary and secondary FRI endpoints ^b and mucus plugs score versus conventional lung function measures (pre-BD FEV ₁ and pre-BD FVC) at week 0. Estimated increases in primary and secondary FRI endpoints ^b and mucus plugs score for every one percent increase in pre-BD FEV ₁ and pre-BD FVC at week 0.							

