9.4.2.2 Secondary Objectives

For the secondary objective 1, univariate paired *t*-tests and mixed effects modelling will be used to assess whether there are statistically significant differences in the means of secondary FRI endpoints (untrimmed total mucus plugs score at TLC, untrimmed total air trapping at FRC, trimmed distal iVaww at TLC, trimmed distal siVaw at TLC and FRC, and untrimmed total iVlung at TLC and FRC) at week 0 vs week 13, unadjusted for patient characteristics.

Secondary analysis of each secondary endpoint will be a mixed-effects model to incorporate the repeated measurements (corresponding to the different lobes) for each subject. The model will estimate the average change from baseline in secondary endpoint at week 0 vs week 13 per lobe, after accounting for the baseline measurement of the secondary endpoint per lobe and heterogeneity across lobes.

For secondary objective 2, a scatter plot will be used to display values of imaging endpoints (primary and secondary FRI parameters) and conventional lung function measures (pre-BD FEV₁ and pre-BD FVC response) at week 0, to get a first indication of the relationship between endpoints at baseline. Spearman's rank correlation coefficients will describe the strength of the association between two endpoints. Pearson correlation will also be used for linear relationships. Regression models will be used to estimate the average increase in imaging endpoints per unit increase in conventional lung function measures, with 95% confidence intervals.

For secondary objective 3, a scatter plot will be used to display changes from baseline at

week 13 in imagine endpoints (primary and secondary FRI parameters) against changes from baseline at week 13 in conventional lung function measures (pre-BD FEV₁ and pre-BD FVC response). Both Spearman's rank and Pearson correlation coefficients will describe the strength of the association. If changes from baseline in conventional lung function measures at week 13 are related to baseline values, as indicated by fitted regression models, correlation coefficients will be reported per subgroup defined by baseline value.

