3 STATISTICAL ANALYSIS

This section provides information on definitions, derivation and analysis/data presentation per domain.

All continuous variables, including FRI parameters (Table 2), pre-BD FEV₁, pre-BD FVC, CCI , will be summarized using means, standard deviation (SD) and 95% ranges, or medians and inter-quartile ranges, depending on the distributions of the data. Mean changes from baseline in continuous variables will be reported, including asymptotic 95% confidence interval (CI). Categorical data (eg, CCI

) will be summarized as the number and

percentage among participants with non-missing data. Descriptive statistics will be calculated for the data stratified by gender. Unless otherwise stated, all hypothesis tests are two-sided and all hypothesis tests will be performed at a 5% significance level. Analyses will be carried out for overall participants and subgroups as specified in Section 3.2.1.8. FRI parameters may be log-transformed prior to analysis to reduce skewness.

All report outputs will be produced using SAS® version 9.4 or a later version in a secure and validated environment.

For continuous data, mean, and upper and lower quartiles will be rounded to one additional decimal place compared to the original data. The SD will be rounded to one additional decimal place compared to the original data. Median, minimum and maximum will be displayed with the same accuracy as the original data. For categorical data, percentages will be rounded to one decimal place, percentages will not be shown for 0, decimal places will not be shown for 100%.

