2.7 Linear Regression Model

In SAP sections 3.2.4 and 3.2.6, it states that more than just the intercept should be displayed in the final outputs however it is the intercept which is of interest and should be reported.

Linear regression models that have a population n < 10 will not be shown in the final outputs.

Throughout the linear regression sections of the SAP there is certain wording that requires more clarity. So, the following sections outline the number of model that should be used for each endpoint.

2.7.1 Secondary Endpoint 3 - Relationship Between Changes from Baseline in Airway Dynamics and Lung Functions Measurements at Week 13

The use of the word unadjusted in the SAP causes confusion over the number of models. Instead, the number of models is outlined explicitly. Three linear models will be fitted for each imaging parameter, where the endpoint will be change from baseline to week 13 in the imaging parameter:

- Model 1: Adjustment for baseline measurement of imaging parameter only
- Model 2: Adjustment for baseline measurement of imaging parameter and for change from baseline to week 13 in pre-BD FEV1
- Model 3: Adjustment for baseline measurement of imaging parameter and for change from baseline to week 13 in pre-BD FVC

CONFIDENTIAL

Developed from TP-BPM-WW-032; related to SOP-BPM-WW-001 D3250R00107

Statistical Analysis Plan Addendum

Table 4outlines the models that are expected for the analysis of tertiary endpoint 1.

Should there be no data for the assigned reference category then the most abundant category will be assigned as the reference.

Table 5 outlines all the of models expected for tertiary endpoint 2

Project Document Version No.: 3.0; Document Effective Date: 03 Sep 24 TP-GDO-WW-169-01 Effective Date: 22 Dec 21 Related to: SOP-GDO-WW-019 CONFIDENTIAL

Developed from TP-BPM-WW-032; related to SOP-BPM-WW-001 D3250R00107

Statistical Analysis Plan Addendum

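### SAP 3.2.3.4 estimates an objective 2 slope only when Pearson's p-value is significant; the protocol sets no such condition, and it inflates the slopes that are shown

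*SAP*

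**What the plan says.** The protocol makes the baseline slopes part of objective 2. Its outcome table (Section 3, Table 2) lists "Estimated increases in primary and secondary FRI endpoints" per one percent increase in pre-bronchodilator FEV1 and FVC. Section 9.4.2.2 states: "Regression models will be used to estimate the average increase in imaging endpoints per unit increase in conventional lung function measures, with 95% confidence intervals". Neither place sets a significance condition. In 9.4.2.2 only the Pearson coefficient is tied to linearity.

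SAP Table 6, which defines Secondary Endpoint 2, lists "Regression coefficients with 95% CI", again without a condition. SAP 3.2.3.4 then makes the regression depend on two things: the linearity assumptions must hold, and the pair must be significantly correlated. In its words, "if the two endpoints are correlated as per Pearson's p-value, a linear regression model will be used to estimate the average increase". That sentence gives no threshold, so the general rule in SAP Section 3 applies: "all hypothesis tests are two-sided and all hypothesis tests will be performed at a 5% significance level". Later in 3.2.3.4 the wording is unconditional: "Two models will be fitted for each imaging endpoint".

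The SAP amendment history records only an analysis-set change for Secondary Endpoint 2. The addendum does not list the condition among its changes from the protocol. Its Section 2.7 revises other regression rules and adds "Linear regression models that have a population n < 10 will not be shown in the final outputs", but leaves the p-value condition in place.

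**The concern.** Whether a listed outcome measure is estimated would depend on the data, through the same test that judges the estimate. Where the true relationship is weak, a slope reaches the table only in samples that happened to overstate it. The usual 95% interval takes no account of that selection.

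Two things are at stake. A published slope, such as millilitres of mucus per unit of FEV1, could be taken as an ordinary unselected estimate. And 3.2.3.4 can be programmed in two ways, one following the p-value condition and one following the sentence that every imaging endpoint gets two models, so the tables could differ.

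**Working it through.** **Inputs**
- Threshold: two-sided 5% (SAP Section 3).
- Analysis set: the baseline endpoints set (SAP Table 6). Its size is not stated. The protocol synopsis estimates 38 enrolled, 34 evaluable and 29 in the primary population, so 34 is the central value and 29 to 38 the range.
- Pairs: 8 FRI parameters × 2 lung function measures = 16.
- True correlation r: no expected value is given for these pairs, so a range is assumed.

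**Step 1: the two tests are the same.** In a one-covariate regression, slope ÷ SE(slope) = r√(n−2)/√(1−r²), which is the Pearson t statistic. A pair passes only if its sample correlation exceeds t/√(t²+n−2) in absolute value:
- n = 29: 2.052/√(4.21+27) = 0.367
- n = 34: 2.037/√(4.15+32) = 0.339
- n = 38: 2.028/√(4.11+36) = 0.320

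If the true correlation is 0.2 and n = 34, the smallest correlation that passes is already 0.339/0.2 = 1.7 times the truth.

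**Step 2: the plan's nominal figure, without the condition.** In 150,000 simulated bivariate normal data sets per cell (unit SDs, so the true slope equals r), the mean slope equalled the truth. The 95% interval covered in 94.8% to 95.1% of data sets in every cell. The nominal 95% is reproduced.

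**Step 3: the same data, keeping only slopes with p < 0.05, n = 34.**

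| True r | Slope shown | Mean shown slope ÷ truth | Coverage of shown intervals |
|---|---|---|---|
| 0.1 | 8.7% | 3.6 | 64% |
| 0.2 | 20.7% | 2.1 | 87.5% |
| 0.3 | 41.6% | 1.5 | 94.0% |
| 0.35 | 54.0% | 1.3 | 95.4% |
| 0.4 | 66.7% | 1.2 | 96.1% |
| 0.5 | 87.4% | 1.07 | 96.8% |
| 0.6 | 97.5% | 1.01 | 95.9% |

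At r = 0 the signed mean stays at zero by symmetry. The mean absolute shown slope is 0.40, and no shown interval covers the truth.

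**Step 4: range of n.** Going from n = 29 to n = 38, r = 0.2 gives 2.3 to 2.0 times and 85% to 88% coverage; r = 0.3 gives 1.6 to 1.4 times and 93% to 95%. SAP 3.2.3.7 carries the analysis into subgroups. At an assumed subgroup size of 15, r = 0.2 gives 2.9 times and 74%.

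**Step 5: skewed data.** Mucus volume was simulated with 20% or 40% zeros (assumed) and a long right tail, then analysed as log(x+1) as in Addendum 2.11.3, with n = 34. True correlations of 0.22 to 0.23 gave 1.9 to 2.0 times and 89% to 91% coverage. Without the condition, coverage was 94% to 96%. The result does not depend on normality.

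**Step 6: null pairs.** If all 16 pairs were truly uncorrelated, 16 × 0.05 = 0.8 slopes would still be shown on average. If the pairs were independent, the chance of at least one would be 1 − 0.95¹⁶ = 56%.

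The linearity condition was not simulated.

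**The case against.** **The selection is visible.** Scatterplots and Spearman coefficients, and Pearson coefficients where the relationship looks linear, are reported for every pair with intervals and p-values. A careful reader could see why a slope is missing. This stands and limits the harm, but it does not correct the slopes and intervals that are shown.

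**The internal conflict may be only apparent.** Table 6 is shorthand: it also lists Pearson correlation without the linearity condition that 3.2.3.4 puts on it. The sentence on two models can be read as a count (one for FEV1, one for FVC) once the condition is met. That reading is possible, so the conflict within the SAP is a matter of ambiguous wording. The departure from the protocol does not depend on it.

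**The central pair may not be weakly correlated.** Protocol 4.2 cites a cohort in which plugs in four or more segments were found in 67% of patients with FEV1 below 60% predicted and 19% of those at 60–80%. If a share f of participants is below 60%, phi = 0.48√(f(1−f))/√(p(1−p)) with p = 0.19 + 0.48f. This gives 0.42 at f = 0.2, 0.48 at f = 0.5 and 0.44 at f = 0.7, where the distortion is modest. The point is fair for mucus against FEV1. It concerns a plug score in an external cohort and says nothing about the other FRI parameters or FVC.

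**n = 29 is too low for this set.** As planned, the baseline set contains the 34 evaluable participants. However, Addendum 2.14 drops participants parameter by parameter when scans are incomplete, so smaller numbers remain possible. The conclusion holds at 34 and 38 in any case.

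**Keeping the linearity check leaves another condition the protocol lacks.** This is correct. Removing the p-value condition cures only the significance selection. A linearity check is not a filter on the size of the estimate.

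**Conclusion.** The concern holds. SAP 3.2.3.4 makes a protocol-listed outcome measure conditional on its own significance, and no document declares this as a change. Shown slopes are inflated on average: about twofold at a true correlation of 0.2, by half at 0.3, and negligibly by 0.6. Their intervals under-cover when the true correlation is below about 0.35, and not above it. These sizes assume a 5% two-sided threshold, 29 to 38 participants and a range of true correlations that the documents do not fix.

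The reach is limited to the slopes of a descriptive secondary objective. The correlations, the primary analysis and the safety analyses are unaffected. It should be changed, but it does not threaten the trial's main result.

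**What to change.** In SAP 3.2.3.4, delete the condition that the pair be correlated by Pearson's p-value, so that the linearity check is the only condition left in that sentence. Report the slope with its 95% interval for each of the 16 pairs that passes the check, whatever its p-value. This restores the protocol's freedom from any significance condition and removes the p-value conflict with Table 6 and with the later sentences of 3.2.3.4.

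The cost is one deleted clause and a few more table rows. No new data or method is needed.

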3.2.3.5 Sensitivity Analyses of the Secondary Endpoint

Not applicable.

3.2.3.6 Supplementary Analyses of the Secondary Endpoint

Not applicable.

3.2.3.7 Subgroup Analyses

Subgroup analyses will be carried out as described in Section 3.2.1.8.

3.2.4 Secondary Endpoint 3 - Relationship Between Changes from Baseline in Airway Dynamics and Lung Functions Measurements at Week 13

3.2.4.1 Definition

Table 7Definition of Secondary Endpoint 3

Population:	Primary analysis population
Endpoints:	 Relationship between change from baseline (Week 0 to 13) in: pre-BD FEV₁ and each FRI parameter (primary and secondary) pre-BD FVC and each FRI parameter (primary and secondary)
Treatment:	Benralizumab 30 mg, 3 doses, once every 4 weeks (at baseline [V1], Week 4 [V2], and Week 8 [V3])
Intercurrent events:	Participant withdrawal, IPD, use of prohibited medicines/substances, asthma exacerbation (participants with exacerbations will be excluded from the primary analysis set)

Population-level	•	Spearman's rank correlation coefficients
summary:	•	Pearson correlation
	•	Graphical summary (scatterplots)
	•	Regression coefficients with 95% CI

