9.2 Sample Size Determination

Note: "Enrolled" means a participant's, or their legally acceptable representative's, agreement to participate in a clinical study following completion of the informed consent process. Potential participants who are screened for the purpose of determining eligibility for the study, but are not assigned in the study, are considered" screen failures", unless otherwise specified by the protocol.

9.3 **Populations for Analyses**

The following populations are defined:

Population/Analysis set	Description		
Enrolled	All participants who sign the informed consent form		
Randomly assigned to study intervention	NA (single-arm study)		
Evaluable	All participants who have completed three doses of investigational product, and have baseline and post-benralizumab treatment study evaluation (PROs, CT scans and spirometry tests) - the evaluable population.		
Primary analysis population	The portion of the evaluable population that did not have an acute asthma exacerbation nor lower respiratory tract infection during the study period will be the primary analysis population for the endpoints in this study.		
Baseline endpoints analysis set	Participants who have baseline measurements and who have had at least one dose of investigational product, irrespectively of whether they discontinued for reasons described in Section 7.1 will be included for analyses conducted on the study population who at least started treatment.		
Safety analysis setThe Safety analysis set consists of all participants who have receive one dose of investigational product.			

Table 8Populations for Analysis

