9.4.4 Other Analyses

Further analyses will be conducted for the secondary objectives related to crosssectional associations between imaging (FRI) endpoints and conventional lung function measurements (FEV₁ and FVC) at week 0. These analyses will use measurements from the study population that includes both participants who completed the study per protocol definition, and those who completed baseline measurements at Visit 1 and had at least one dose of IP irrespectively of whether they discontinued for reasons described in Section 7.1.

CCI

The evaluable population (Table 4) will be analyzed for the same outcome measures conducted for the primary analysis population (Table 4).

Additional analyses will be conducted for all outcome measures for both the primary analysis population and the evaluable population for the following subgroups:

- Mucus plugging status: Participants with or without mucus plugs identified at the CT scans (Section 8.1.1.2) at Visit 1 (week 0)
- OCS dependency status: OCS-dependent and Non-OCS-dependent participants as defined by the inclusion criteria #4 (Section 5.1)

Results from subgroup analyses above will be compared with corresponding results from the evaluable population.

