Section 3.6.2: Adverse events	09/11/2023	AEs collection dates specified	Yes (v 4.0)	Clarification required
Section 5: References	09/11/2023	New references added	Yes (v 4.0)	Clarification required
Section 6: Appendix	09/11/2023	New appendix added	Yes (v 4.0)	Clarification required
Section 2.3: General considerations	22/01/2024	Table 2 edited: proposed rank removed; abbreviations added, endpoints with proposed rank >7 removed except con	Yes (v 5.0)	Updated as in CSP
Section 3.2: Endpoint analysis	22/01/2024	Table 3 edited, clarification of some endpoints	Yes (v 5.0)	Clarification required
Section 3.2.1: Primary Endpoint – Change from Baseline (Week 0) to week 13 in airway dynamics, using untrimmed total mucus volume at TLC	22/01/2024	Changes to endpoints	Yes (v 5.0)	Endpoint changes to CSP v 5.0
Section 3.2.1.5: Secondary analysis of primary endpoint	22/01/2024	Mixed model equation added	Yes (v 5.0)	Clarification required

STATISTICAL ANALYSIS PLAN D3250R00107 – ed. 2.0

CATEGORY Change refers to:	Date	Description of change	In line with CSP?	Rationale
Section 3.1.6.1 Disease characteristics. Definitions and derivations	12/02/2024	Imputation rules added	Yes (v 5.0)	Clarification required
Section 3.2.4 Secondary Endpoint 3	13/02/2024	Analysis set removed, except Primary analysis set	Yes (v 5.0)	Population removed to streamline analysis
Section 3.2.5 Tertiary Endpoint 1	13/02/2024	Analysis set removed, except Baseline endpoints analysis set	Yes (v 5.0)	Population removed to streamline analysis
Section 3.2.6 Tertiary Endpoint 2	13/02/2024	Analysis set removed, except Primary analysis set	Yes (v 5.0)	Population removed to streamline analysis
Section 3.2.3 Secondary Endpoint 2	16/02/2024	Analysis set removed, except Baseline endpoints analysis set	Yes (v 5.0)	Population removed to streamline analysis

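### The SAP drops the evaluable-set analysis of secondary objective 3 that Protocol 9.4.4 requires, and logs the change as in line with the protocol

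*SAP*

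**What the plan says.** **Protocol.** Section 9.3 (Table 8) defines the primary analysis population as "The portion of the evaluable population that did not have an acute asthma exacerbation nor lower respiratory tract infection during the study period", and makes it the primary set for the study's endpoints. Section 9.4.4 then adds two requirements. The first is general: "The evaluable population (Table 4) will be analyzed for the same outcome measures conducted for the primary analysis population". The second concerns mucus plugging status and OCS dependency: "Additional analyses will be conducted for all outcome measures for both the primary analysis population and the evaluable population for the following subgroups". The table number cited in 9.4.4 is wrong (Table 4 lists restricted medicines, and the populations are in Table 8), but the meaning is clear. A redacted block precedes these sentences. The sentences themselves are unqualified, and no readable text exempts secondary objective 3.

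**SAP.** For secondary objective 3, both Table 3 and the Population row of Table 7 (Section 3.2.4.1) give "Primary analysis population" and nothing else. The intercurrent-event row of Table 7 lists "asthma exacerbation (participants with exacerbations will be excluded from the primary analysis set"). The amendment history entry for Section 3.2.4, dated 13/02/2024, gives the reason as "Population removed to streamline analysis" and answers yes (v 5.0) to whether the change is in line with the CSP.

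**SAP Addendum.** Section 1, which lists changes from the CSP, does not mention this departure. Section 2.7.1 sets out Models 1 to 3 for this endpoint without restoring the evaluable set.

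**The concern.** The SAP says it is based on protocol version 5.0, so a reader expects every outcome analysed in the primary population to be repeated in the evaluable population. For this objective it is not, and the log tells the reader that nothing has departed from the protocol.

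The objective carries weight. Protocol 4.2 says that positive correlations between changes in lung function and change in the primary endpoint would support a clinically meaningful benefit. In an uncontrolled trial this is one of the main links between the imaging result and anything clinical. Membership of the primary set depends on events after treatment starts, so the link is estimated only in participants who stayed free of exacerbation and lower respiratory tract infection. Without the evaluable-set version, nobody can see whether the relation changes when the others are included.

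**Working it through.** **1. Populations by endpoint.**

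| Endpoint | Protocol 9.4.4 | SAP |
|---|---|---|
| Primary endpoint | primary and evaluable | both (Table 4) |
| Secondary endpoint 1 | primary and evaluable | both (Table 5) |
| Secondary endpoint 3 | primary and evaluable | primary only (Tables 3 and 7) |

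The wording about excluding participants with exacerbations also appears in SAP Tables 4 and 5. There it does no harm, because the evaluable set is listed beside the primary set. The defect in Table 7 is therefore its Population row. SAP 3.2.4.3 and 3.2.4.4 still speak of populations in the plural, which fits a set having been taken out.

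**2. Can the omitted participants have the data?** Yes. Under Protocol 8.3.1, a participant with a non-hospitalised event between Visits 1 and 3 follows the normal schedule, and one with an event between Visits 3 and 4 may still have the Visit 4 assessments. Such a participant, if fully dosed, can be evaluable with paired scans and spirometry.

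**3. How many?** The synopsis plans 38 enrolled, 34 evaluable and 29 in the primary analysis population. The 29 cannot be reproduced, because the inputs in Protocol 9.2 are redacted. The counts imply:

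- enrolled to evaluable: 1 − 34/38 = 10.5% lost;
- evaluable to primary: 34 − 29 = 5, and 5/34 = 14.7%.

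The 5 combine exacerbations and lower respiratory tract infections. Addendum 1.1 now admits a participant to the evaluable set with any one of PROs, CT or spirometry, so some may lack the paired data this objective needs. The figure is therefore up to 5.

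**4. Precision.** The 95% interval for a correlation r is tanh(atanh r ± 1.96/√(n − 3)). At r = 0.50, atanh r = 0.549.

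- n = 29: half-width 1.96/√26 = 0.384, interval 0.16 to 0.73.
- n = 34: half-width 1.96/√31 = 0.352, interval 0.19 to 0.72.

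**5. Possible shift in the correlation (assumed values).** Take r = 0.40 and unit variances within both groups, with the omitted fraction p = 5/34 differing in mean by k SD on both change scales. Then p(1 − p) = 0.1254, and

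r(evaluable) = (0.40 ± 0.1254k²) / (1 + 0.1254k²),

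with plus when the two shifts are in the same direction and minus when they are opposite.

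| k | Same direction | Opposite directions |
|---|---|---|
| 0.5 | 0.418 | 0.357 |
| 1 | 0.5254/1.1254 = 0.467 | 0.2746/1.1254 = 0.244 |

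With k = 2 in the same direction, (0.40 + 0.502)/(1 + 0.502) = 0.60. The exclusion could hide a stronger relation or make a weaker one look stronger.

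**The case against.** **Only a supportive analysis is missing.** Protocol Table 8 makes the event-free set primary for the endpoints, and the evaluable repeat sits under Other Analyses. Protocol 8.3 also gives a reason for the exclusion: exacerbations, respiratory infections and their treatments may alter airway inflammation. This stands. A reader might infer that the main analysis of objective 3 was changed, or that these participants drop out of the trial's results altogether. Neither is so: the main set is as the protocol defines it, and evaluable participants still enter the evaluable-set analyses of the primary endpoint and secondary endpoint 1.

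**The direction of bias is not established.** A reader might infer that leaving these participants out weakens the correlation, on the view that they respond poorly on both scales. If they were exactly the lowest 5/34 on FEV1 change in a bivariate normal, the retained variance would be about 0.64 and a correlation of 0.50 would fall to 0.42. The documents do not support that picture. Events that required hospitalisation lead to discontinuation (Protocol 7.1 and 8.3.1), so evaluable participants with an event are probably the milder cases. Some would be assessed 7 to 14 days after OCS or antibiotics, which could move either measure either way. The 0.42 is not a bound, as the 2 SD case in the check shows. And if selection acted only through FEV1 change, a correctly specified regression on FEV1 change would keep unbiased coefficients even though the correlation shrank.

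**The gain in precision is slight and the objective is descriptive.** Also true. The case rests on conformity with the protocol and on selection after baseline.

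**The removal could be declared instead.** Recording it as a reasoned departure from 9.4.4 would settle the inconsistency between documents. It would not supply the missing check.

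**Conclusion.** The point holds as a departure from Protocol 9.4.4 that is recorded as conformity. The SAP keeps the protocol's primary set for secondary objective 3 but drops the required evaluable-set analysis, overall and by subgroup.

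Up to 5 of a planned 34 participants, about 15%, enter no analysis of the objective. That count rests on planning estimates, covers lower respiratory tract infection as well as exacerbation, and would be lower where paired CT or spirometry is missing. The effect on the correlation cannot be given a size or a sign from the documents; the range of 0.24 to 0.47 around 0.40 illustrates assumed 1 SD shifts and is not an estimate.

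A reader might extend the finding to SAP 3.2.6, which also uses the primary analysis population only. That endpoint and its protocol objective are redacted, so the same departure cannot be asserted there.

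**What to change.** - In SAP Table 3 and Table 7, restore the evaluable set beside the primary analysis population for secondary objective 3.
- Report the correlations and Addendum Models 1 to 3 in both sets, including the two subgroup factors in Protocol 9.4.4, subject to the addendum's rule that regression models with n < 10 are not shown.
- Mark participants with an exacerbation or lower respiratory tract infection on the scatter plots.
- Correct the amendment-history entry that calls the removal in line with the CSP.
- Check, against the unredacted protocol, whether SAP 3.2.6 needs the same change.

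The evaluable set is already built for the primary endpoint and secondary endpoint 1, so the cost is a few more tables from existing programs, with no new data.
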